# 7.3.5. Completion (discontinuation) record

If the administration of this product is completed or discontinued, the reason will be recorded excluding the case where the administration is continued.

If an adverse event is selected for the reason, the information in detail should be recorded in the adverse event column.

[Reason for completion]

- Completion of prophylaxis
- If the objective of administration is changed from prophylaxis to treatment, completion of administration of this product for treatment.

[Reason for discontinuation]

- For the onset of invasive fungal infections
- Adverse events (other than invasive fungal infections)
- No return to hospital
- Hospital transfer
- Other

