# 7.5. Study size

#### 7.5.1. Planned sample size

200 patients (100 patients each for children and adults)

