#### Effectiveness perspectives:

The successful rate of prophylaxis at Day 100 in the phase 3 study of prophylactic administration (study A1501073) was 54.3% (121/223 patients) and the successful rate of prophylaxis at Day 180 was 48.9% (109/223 patients). Presuming that the 50% prophylactic effect can be obtained at Day 180 by referring to the above results, the 95% CI will be 40 - 60% if the target sample size is set to be 100 patients and 43-57% if the target sample size is set to be 200 patients. The prophylactic effect can be confirmed at the estimate accuracy of about  $\pm 10\%$  if 100 patients for whom this product is administered for prophylaxis of invasive fungal infections are accumulated and that of about  $\pm 7\%$  if 200 patients are accumulated.

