#### (2) Effectiveness analysis

The proportion of patients who developed invasive fungal infections (the number of patients with proven diagnosis + the number of patients with probable diagnosis/number of patients for effectiveness analysis excluding undeterminable patients  $\times$  100), proportion of patients with successful prophylaxis of invasive fungal infections (the number of patients without onset of invasive fungal infections/the number of patients for effectiveness analysis excluding undeterminable patients  $\times$  100), and each 95% CI will be calculated for effectiveness analysis set. Also, the analysis using the survival analysis method (Kaplan-Meier method) will be performed.

Detailed methodology for summary and statistical analyses of data collected in this study will be documented in a Statistical Analysis Plan (SAP), which will be dated, filed and maintained by the Sponsor. The SAP may modify the plans outlined in the protocol; any major modifications of primary endpoint definitions or their analyses would be reflected in a protocol amendment.

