The successful rate of prophylaxis at Day 100 in the phase 3 study of prophylactic administration (study A1501073) was 54.3% (121/223 patients) and the successful rate of prophylaxis at Day 180 was 48.9% (109/223 patients). Presuming that the 50% prophylactic effect can be obtained at Day 180 by referring to the above results, the 95% CI will be 40-60% if the target sample size is set to be 100 patients and 43-57% if the target sample size is set to be 200 patients. The prophylactic effect can be confirmed at the estimate accuracy of about $\pm 10\%$ if 100 patients for whom this product is administered for prophylaxis are accumulated and that of about $\pm 7\%$ if 200 patients are accumulated.

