8.1.3. Analysis of Binary Data

The frequency and proportion will be calculated. If the confidence interval of proportion is calculated, two-sided 95% confidence interval (exact method) will be calculated.

If the proportion is compared between subgroups, risk ratio and its 95% confidence interval, and risk difference and its 95% confidence interval will be calculated. In addition, risk ratio and its 95% confidence interval will be graphically presented (see Appendix 2). If the number of patients in at least one category compared is \leq 5, the number of patients and proportion will be calculated but risk ratio and its 95% confidence interval, and risk difference and its 95% confidence interval will not be calculated.

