8.2.4. Effectiveness Analysis

8.2.4.1. Proportion of Patients Who Developed Invasive Fungal Infections (IFI rate)

In the effectiveness analysis set, the proportion of patients who developed invasive fungal infections (%) and its 95% confidence interval will be calculated. The calculation formula is shown below.

Proportion of patients who developed invasive fungal infections (%) = [(number of patients with proven diagnosis + number of patients with probable diagnosis)/number of patients for effectiveness analysis excluding undeterminable patients] \times 100

For each of the following factors specified in Section 5.4, the same subgroup analyses will be performed.

- Indication for transplantation
- Objective of treatment [primary prophylaxis, secondary prophylaxis]
- Age (1) [\leq 15 years, \geq 15 years]
- Age (2) [<65 years, ≥ 65 years]
- Hepatic dysfunction [absent, present, unknown]
- Renal dysfunction [absent, present, unknown]
- Long-term treatment [<180 days, ≥180 days]

8.2.4.2. Proportion of Patients with Successful Prophylaxis of Invasive Fungal Infections (Success rate)

In the effectiveness analysis set, the proportion of patients with successful prophylaxis of invasive fungal infections (%) and its 95% confidence interval will be calculated. The calculation formula is shown below.

Proportion of patients with successful prophylaxis of invasive fungal infections (%) = (number of patients without onset of invasive fungal infections/number of patients for effectiveness analysis excluding undeterminable patients) \times 100

For each of the following factors specified in Section 5.4, the same subgroup analyses will be performed.

- Indication for transplantation
- Objective of treatment [primary prophylaxis, secondary prophylaxis]
- Age (1) [<15 years, ≥ 15 years]
- Age (2) [<65 years, ≥ 65 years]
- Hepatic dysfunction [absent, present, unknown]
- Renal dysfunction [absent, present, unknown]
- Long-term treatment [<180 days, $\geq 180 \text{ days}$]

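### The prophylaxis success rate can fail only through infection before administration ends, so uninfected patients who stop for an adverse event or die are never failures, and the rate is not the Day 180 rate used for planning

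*SAP*

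**What the plan says.** - **Formula.** SAP 8.2.4.2 takes "number of patients without onset of invasive fungal infections/number of patients for effectiveness analysis excluding undeterminable patients", times 100. Protocol 7.7, effectiveness analysis, has the same ratio: "the number of patients without onset of invasive fungal infections/the number of patients for effectiveness analysis excluding undeterminable patients". For the interval, SAP 8.1.3 states "two-sided 95% confidence interval (exact method) will be calculated".
- **Outcome levels.** Protocol 7.3.6.1 and SAP 6.2 allow three ratings: without onset, with onset (proven, probable or possible) and undeterminable. A reason is recorded for undeterminable, but no rule says when that rating applies.
- **Window.** Under Protocol 7.2.6 the observation period runs from the first to the last day of administration, limited by the end of the investigation. SAP 6.2 judges onset within that period.
- **Analysis set.** SAP 5.2 removes patients with no effectiveness assessment or a non-target disease. It sets no minimum exposure and does not exclude early stops or deaths.
- **Reason for ending.** Protocol 7.3.5 records completion of prophylaxis separately from discontinuation, whose reasons include "Adverse events (other than invasive fungal infections"). Death is not a listed reason. SAP 8.2.1 tabulates reasons and timing in the safety set. SAP 9 lists deaths.
- **Planning value.** Protocol 7.5.2 says: "Presuming that the 50% prophylactic effect can be obtained at Day 180 by referring to the above results". SAP 2.1 gives the source, study A1501073: "the successful rate of prophylaxis at Day 180 was 48.9% (109/223 patients"). It then states that "the 95% CI will be 40-60% if the target sample size is set to be 100 patients and 43-57"% for 200. The target in Protocol 7.5.1 is "200 patients (100 patients each for children and adults").

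**The concern.** The label says prophylaxis succeeded, but the formula measures only that no infection was recorded while the product was being given. A patient taken off in the first week for hepatic toxicity, with no infection by then, meets the definition. So does a patient who dies uninfected on treatment. If the physician rates such a patient undeterminable, the patient disappears from the ratio instead.

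This matters because discontinuation after hepatic toxicity or visual events is something the study is designed to examine (Protocol 7.3.8). One of its two effectiveness proportions is blind to that outcome, and no planned table links onset status to the reason treatment ended.

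The time point adds a second difficulty. The 50% is a Day 180 figure. The study's rate is read at the end of each patient's treatment, whenever that falls, so shorter treatment leaves less time for an infection to be counted.

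**Working it through.** **1. The plan's own figures reproduce.** 121/223 = 54.3% and 109/223 = 48.9%. With 0.5 ± 1.96·√(0.25/n):
- n = 100: 0.5 ± 0.098, or 40.2–59.8% (exact 39.8–60.2%).
- n = 200: 0.5 ± 0.069, or 43.1–56.9% (exact 42.9–57.1%).

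The precision statement is correct.

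**2. What the formula implies.** Let D be the effectiveness set minus undeterminable patients, and I = (proven + probable + possible)/D. Everyone in D is either without onset or with onset, so success = 1 − I. Possible cases count against success although they are left out of the infection rate in SAP 8.2.4.1. A result of 50% or less needs onset on treatment in at least half of D, for example 100 of 200.

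**3. Effect of how early stops and deaths are rated.** All counts are assumed: 200 patients, of whom a have onset and b are uninfected early stops or deaths.

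| a | b | Rated without onset: (200−a)/200 | Rated undeterminable: (200−a−b)/(200−b) | Counted as failures: (200−a−b)/200 |
|---|---|---|---|---|
| 20 | 20 | 90.0% | 160/180 = 88.9% | 80.0% |
| 20 | 60 | 90.0% | 120/140 = 85.7% | 60.0% |
| 20 | 80 | 90.0% | 100/120 = 83.3% | 50.0% |
| 40 | 60 | 80.0% | 100/140 = 71.4% | 50.0% |

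In the first of the three result columns, b has no effect at all.

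**4. Document-based figures for one cause of stopping.** Protocol 7.5.2 gives discontinuations among patients with hepatic reactions. As fractions of all patients in each study they are 1/233 = 0.4%, 2/45 = 4.4% and 2/21 = 9.5%. If all 200 patients are determinable and these would otherwise be rated without onset, counting them as failures lowers the rate by 0.4 to 9.5 percentage points, about 1 to 19 patients. Other adverse-event stops and deaths are not included, and the documents give no rate for them.

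**5. Effect of reading at end of treatment.** Assume a constant infection hazard h = −ln(1−q)/180, where q is the 180-day risk, and exponential stopping for any reason at rate g = ln 2/median, with follow-up ended at 180 days. The proportion infected on treatment is h/(h+g)·(1 − exp(−180(h+g))).

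| q (assumed) | All treated 180 days | Median 60 days | Median 30 days | Median 15 days |
|---|---|---|---|---|
| 20% | 80% | 91% | 95% | 97% |
| 40% | 60% | 82% | 89% | 94% |

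The infection hazard is constant along each row, so only treatment duration moves the score. This series shows the time-point difference. It does not isolate stopping for toxicity or death, because ordinary completion shortens exposure in the same way.

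**6. Position relative to 50%.** By step 2, the expected rate exceeds 50% exactly when I is below 50%. At n = 200 the chance that the observed rate exceeds 50% is at least 0.997 for I from 5% to 40%, 0.91 at 45%, 0.47 at 50% and 0.07 at 55%. All values of I are assumed.

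**The case against.** **A reader might infer that an inert product would beat the planned 50%.** The documents do not support that as a fact. It requires on-treatment onset below 50% without an effective product, and no untreated infection rate is given. Nor would beating 50% trigger anything. SAP 4.1 calls the study non-confirmatory with no significance level, SAP 4.2 has no decision rules, and the 50% is used to plan interval width.

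**A reader might infer that every early stop or death is scored a success.** The documents do not go that far, because the physician may record undeterminable. What stands is that neither rating makes the patient a failure.

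**A reader might infer that the definition differs from that of study A1501073.** This cannot be shown, since its definition is absent. What can be shown is that the definition is missing and that the time points differ.

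**Other analyses partly expose short treatment.** SAP 8.2.4.3 plans Kaplan-Meier analyses of proven/probable onset and of any onset, censoring uninfected patients at end of treatment, so early stops are not scored as successes there. SAP 8.2.4.4 applies the duration bands of SAP 5.4 to both proportions. These help, but neither uses the reason for stopping. The Kaplan-Meier analysis treats stopping for toxicity and death as ordinary censoring, and SAP 8.1.4 specifies quartiles and a plot, not a Day 180 estimate.

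**Tolerability is analysed separately, and no single-arm proportion can establish efficacy.** Both points are fair. They argue for keeping the onset-free proportion and naming it accurately, not for leaving it labelled as success.

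**Conclusion.** The point holds as a problem of definition, labelling and interpretation. Among determinable patients, infection onset up to the end of administration is the only route to failure. Uninfected adverse-event stops and deaths are either successes or absent from the denominator, with no rule to decide which. The rate is read at end of treatment, and no planned proportion estimates the Day 180 quantity behind the 50%.

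The size depends on how many such patients there are. The only document-based figures, for hepatic discontinuations alone, imply a shift of 0.4 to 9.5 points. The assumed case of 60 uninfected early stops or deaths in 200 implies 30 points (90.0% against 60.0%). The sample-size arithmetic is correct and is not affected.

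**What to change.** 1. Keep the formula in SAP 8.2.4.2 and Protocol 7.7, but label it as the proportion free of onset during administration.
2. Cross-tabulate onset status (without onset, proven, probable, possible, undeterminable) by recorded reason for completion or discontinuation and by death, overall and by Age (1). Death must come from the data behind the death listing, because Protocol 7.3.5 has no such reason.
3. Add a supplementary rate with an exact 95% interval on the same denominator: patients without onset who neither discontinued for an adverse event nor died during administration. Show hospital transfer, no return, other reasons and treatment ongoing at study end as separate rows, not counted as failures. Patients rated undeterminable stay outside both rates, so the cross-tabulation is needed to show how many of them stopped for an adverse event or died.
4. Do not set the onset-free proportion beside 54.3% or 48.9% unless the report shows that definition and time point match.

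Cost: wording changes in both documents and one extra table, using onset status, stopping reason and deaths that the plan already collects or lists. The supplementary rate will be lower than the present one whenever an uninfected patient stops for an adverse event or dies.

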8.2.4.3. Analysis of Period Data

In the effectiveness analysis set, time to event onset will be summarized in accordance with Section 8.1.4 with the onset of invasive fungal infections (patients with proven diagnosis + patients with probable diagnosis) considered as an event. Similarly, time to event onset will be summarized in accordance with Section 8.1.4 with the onset of invasive fungal infections considered as an event. Patients without onset will be right-censored at the end of treatment.

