# 7.2.1. Inclusion criteria

- 1. Patients who have not developed invasive fungal infections at the time of initiation of administration of this product (patients with medical history of invasive fungal infections can be registered)
- 2. Patients with history of hematopoietic stem cell transplantation or patients who plan to receive hematopoietic stem cell transplantation

The indications and dosage and administration of this product are as follows. The latest package insert should be referred to when administering this product.

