# 7.2.6. Observation period

The observation period shall start on the day the administration of this product begins and ends on the day the administration is completed; provided that the patients will be followed until the last day of the investigation period as long as possible if the administration period prolongs.

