8.1.4. Analysis of Period Data (Time to Event Onset)

The median, first quartile, and third quartile by Kaplan-Meier method will be calculated. In addition, Kaplan-Meier plots will be prepared.

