9. LISTINGS

The following listings will be prepared. Listings with [Intext] specified after the table name are in a format which allows attachment to the report.

Listing of patients⁴

⁴: Estimated creatinine clearance and eGFR before administration will be added to the patient listing. Refer to Appendix 10.3 for calculation method.

- Listing of patients with adverse events
- Listing of patients with adverse drug reactions
- Listing of patients with adverse drug reactions among pediatric patients
- Listing of patients with adverse drug reactions among elderly patients
- Listing of patients with adverse drug reactions among patients with hepatic dysfunction
- Listing of patients with adverse drug reactions among patients with renal dysfunction
- Listing of patients with adverse drug reactions among patients excluded from the safety analysis set
- Listing of patients with serious adverse drug reactions [Intext]
- Listing of deaths [Intext]
- List of events corresponding to safety specifications
- List of adverse drug reactions falling under safety specifications [Intext]
- Listing of laboratory values
- Listing of patients evaluated for effectiveness
- Listing of the status of treatment of Vfend and plasma voriconazole concentration
- List of contraindicated patients
- Listing of prior treatment (antifungal agents administered for prophylaxis of invasive fungal infections)
- Listing of other reasons for discontinuation [Intext]
- Listing of concomitant medications by patient [Intext]

Furthermore, tables corresponding to appendix tables for periodic safety report (PSUR) and application for reexamination will be prepared in accordance with the notification.

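### The Kaplan-Meier curve for infection onset censors infection-free deaths, so it is a cause-specific on-treatment summary and its complement should not be read as infection incidence

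*SAP*

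**What the plan says.** SAP 8.2.4.3 plans two time-to-onset analyses in the effectiveness analysis set. The first is run "with the onset of invasive fungal infections (patients with proven diagnosis + patients with probable diagnosis) considered as an event". The second takes any onset: "Similarly, time to event onset will be summarized in accordance with Section 8.1.4 with the onset of invasive fungal infections considered as an event". One censoring rule covers both: "Patients without onset will be right-censored at the end of treatment". It does not distinguish why treatment ended.

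The method is set in SAP 8.1.4: "The median, first quartile, and third quartile by Kaplan-Meier method will be calculated", together with plots. Protocol 7.7 says the same in general terms: "Also, the analysis using the survival analysis method (Kaplan-Meier method) will be performed". Neither document mentions a competing event or a cumulative incidence function.

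Three other places bear on how deaths enter the analysis:

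- **Population** (protocol 7.2.1): "Patients with history of hematopoietic stem cell transplantation or patients who plan to receive hematopoietic stem cell transplantation".
- **Follow-up** (protocol 7.2.6): "The observation period shall start on the day the administration of this product begins and ends on the day the administration is completed". SAP 8.2.2 ends the treatment period at the last confirmed administration and counts interruptions as treatment time.
- **Death in the data and outputs:** protocol 7.3.5 does not name death among the reasons for completion or discontinuation. SAP section 9 plans a listing of deaths for the report text, but the time-to-onset analysis makes no use of it.

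**The concern.** Death on treatment ends treatment. Under the rule, a patient who dies without infection leaves the risk set as a censored observation. Kaplan-Meier then treats that patient as someone who could still develop infection later, at the same rate as those remaining. The complement of the curve describes infection risk in a hypothetical setting without death, not the proportion of these patients who develop infection.

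The sample size rationale is framed around a fixed-day quantity, success at Day 180, while the planned effectiveness rates are crude proportions over whatever follow-up each patient had. The curve is therefore the natural place to look for a Day 100 or Day 180 figure. Read that way, it would make prophylaxis look somewhat worse than it was, in results intended for the re-examination application.

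**Working it through.** **1. The plan's own effectiveness figures.** The documents state no figure for the Kaplan-Meier analysis. The only effectiveness precision given is for an assumed 50% success rate at Day 180 (protocol 7.5.2, SAP 2.1). It reproduces:

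- n = 100: 0.5 ± 1.96 × √(0.25/100) = 40.2% to 59.8% (stated 40-60%).
- n = 200: 0.5 ± 1.96 × √(0.25/200) = 43.1% to 56.9% (stated 43-57%).

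These intervals are for a simple proportion, and the present point does not change them.

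**2. How a death is handled.** Follow-up ends with administration, and all patients without onset are censored at end of treatment. An infection-free death on treatment is therefore censored. The SAP does not say so in words, but it follows from the rule. Deaths after treatment has already stopped for another reason fall beyond the censoring date and do not matter here.

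**3. Size.** The documents give neither an on-treatment death rate nor an expected infection rate, so both are assumed. Let F1 be the true Day-180 cumulative incidence of infection and F2 that of infection-free on-treatment death. With constant cause-specific hazards:

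- total cumulative hazard H = −ln(1 − F1 − F2)
- infection share h1 = H × F1/(F1 + F2)
- 1 − KM = 1 − exp(−h1)

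Example with F1 = 5% and F2 = 20%: H = −ln(0.75) = 0.2877; h1 = 0.2877 × 0.05/0.25 = 0.0575; 1 − KM = 5.6%.

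| True infection incidence | Deaths | 1 − KM | Excess (points) | Ratio |
|---|---|---|---|---|
| 5% | 10% | 5.3% | 0.27 | 1.055 |
| 5% | 20% | 5.6% | 0.59 | 1.118 |
| 5% | 30% | 6.0% | 0.97 | 1.194 |
| 10% | 10% | 10.6% | 0.56 | 1.056 |
| 10% | 20% | 11.2% | 1.21 | 1.121 |
| 10% | 30% | 12.0% | 1.99 | 1.199 |

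With 5% deaths the ratio is only about 1.03.

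**4. Against sampling error.** At the planned 200 patients, ignoring censoring, the 95% half-width is 1.96 × √(0.05 × 0.95/200) = 3.0 points at 5% and 1.96 × √(0.10 × 0.90/200) = 4.2 points at 10%. The excess is smaller than this in every row of the table.

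**5. Simulation check.** This used 200 patients, 2,000 runs, and independent exponential end of treatment with mean 60 or 120 days. At F1 = 5% and F2 = 20%, one minus Kaplan-Meier averaged 5.6% and Aalen-Johansen 5.0%, so the latter recovers the true value. Across infection rates of 2-10%, the curve reached the first quartile in about 3-51% of simulated studies and the median in about 1-16%.

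**The case against.** The strongest reply is that the plan does not make the misreading. SAP 8.1.4 asks for the median, quartiles and plots, not a fixed-day complement. Incidence is reported in 8.2.4.1 as a proportion with a confidence interval. A Kaplan-Meier curve censored at end of treatment is a legitimate cause-specific summary, and the protocol specified it. This stands. A reader might infer that the plan overstates infection incidence, but the documents do not support that. The problem arises only if the curve is read as incidence.

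A reader might also expect deaths to make the curve disagree with the crude rate. That is not a fair attribution. Patients are also censored on completing prophylaxis, on transfer, on loss to follow-up and on stopping for adverse events, so the two would differ with no deaths at all. In the simulation at 5% infection and 20% deaths with mean treatment of 60 days, the crude proportion was about 1.8% and Aalen-Johansen 5.0%. The correction is not meant to close that gap.

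Nor is the curve the only analysis that takes any account of follow-up. The SAP also breaks the proportions down by long-term treatment (8.2.4.1, 8.2.4.2) and by treatment-duration bands (5.4, applied in 8.2.4.4), though crudely.

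The size is assumed throughout. The eligible population includes autografts and patients only planning a transplant, so 30% on-treatment deaths is an upper case and not an expectation. The quartiles will often not be reached, so any effect would show mainly in the plots. SAP 4.1 treats the study as non-confirmatory, so no test or error rate is at stake.

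What survives is that the documents neither label the curve as cause-specific nor provide an estimator that can properly be read as incidence over time.

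**Conclusion.** The point holds as one of labelling and completeness. Infection-free on-treatment deaths are censored under SAP 8.2.4.3, so one minus the curve should not be read as infection incidence. The direction is certain whenever such a death precedes a later infection. The size cannot be fixed from the documents. Under constant hazards and assumed deaths of 10-30% by Day 180, the excess is about 0.3-1.0 points over a true 5% and 0.6-2.0 points over a true 10%. A relative overstatement near 20% occurs only at the 30% end of that range.

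The crude infection and success proportions, the sample size and the descriptive tests are untouched. It is a cheap improvement, not a flaw that undermines the effectiveness results.

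**What to change.** In SAP 8.2.4.3:

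1. Add an Aalen-Johansen cumulative incidence of infection for both event definitions (proven plus probable, and any onset), with infection-free death as a competing event and 95% confidence intervals at fixed days such as 100 and 180.
2. State that a patient whose treatment ended because of death counts as a competing event and is not censored at the last dose. Define this by a pre-stated window from last administration to death. Without that rule, censoring at the last confirmed administration can precede the death and leave the estimate unchanged. Safety events are collected to 28 days after last administration (protocol 9.2, SAP 8.2.3), which limits how long the window can be.
3. Report the number of such deaths.
4. Keep the Kaplan-Meier plot required by protocol 7.7, labelled as cause-specific and on-treatment.

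**Cost:** one further standard method to describe and program. Dates of death must be taken from the serious event reports, because protocol 7.3.7 records an event's date of occurrence and outcome but lists no separate date of death. Fatal events are already reportable as serious and deaths are already listed, so no new collection is expected, but completeness of the dates should be checked.
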